22.0 Potential Benefits to Subjects*

22.1 Describe the potential benefits that individual subjects may experience by taking part in the research. Include the probability, magnitude, and duration of the potential benefits. Indicate if there is no direct benefit.

*NOTE: Compensation **cannot** be stated as a benefit.*

Response: Patients who are prescribed antipsychotics often gain significant weight and commonly stop the medication as a result. This can precipitate further psychotic episodes. A program that mitigates the weight gain can improve the health of the patient and the family member (reduced health risks associated with obesity) and reduce the potential for a relapse (which can have multiple social and physical consequences).

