An innovative aspect of this treatment is helping patients develop alternative reinforcements that do not involve food that can reduce the motivation to eat for the hedonic or reinforcing motivations. The first step is to identify alternative activities that have a higher reinforcement value than the patients’ favorite foods. First, participants will identify potential alternatives from the 139 behaviors on the Pleasant Activities List. The therapist then works with the patient to better specify the behavior, ensure its feasibility and describe the parameters of the behavior (e.g. duration). After the participant and case manager agree on a list of alternatives (at least 5), the participant will complete the Behavioral Choice Questionnaire that assesses the reinforcing value of that activity in comparison to food. The most reinforcing food to be used to assess behavioral substitutes will be chosen from a list of usual meals that can be obtained from home cooked, fast food or casual dining restaurants. These alternative reinforcements are used non-contingently by the patients/parents to provide highly desirable activities that compete with excessive food consumption.

6.2 Drug/Device Handling: If the research involves drugs or device, describe your plans to store, handle, and administer those

drugs or devices so that they will be used only on subjects and be used only by authorized investigators.

- *If the control of the drugs or devices used in this protocol will be accomplished by following an established, approved organizational SOP (e.g., Research Pharmacy SOP for the Control of Investigational Drugs, etc.), please reference that SOP in this section.*

Response: NA, the medication that patients are taking will be managed by their physician and only be a screening criteria.

6.3 *If the drug is investigational (has an IND) or the device has an IDE or a claim of abbreviated IDE (non-significant risk device), include the following information:*

- *Identify the holder of the IND/IDE/Abbreviated IDE.*
- *Explain procedures followed to comply with sponsor requirements for FDA regulated research for the following:*

FDA Regulation	Applicable to:		
	IND Studies	IDE studies	Abbreviated IDE studies
21 CFR 11	X	X	
21 CFR 54	X	X	
21 CFR 210	X		
21 CFR 211	X		
21 CFR 312	X		
21 CFR 812		X	X
21 CFR 820		X	

Response: NA

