11.3 List any instruments or measurement tools used to collect data (e.g. questionnaire, interview guide, validated instrument, data collection form).

Include copies of these documents with your submission.

Response: Behavioral Choice Questionnaire, Consideration of Future Consequences Scale, Zimbardo Time Perspective Inventory, Demographic Form for Participant and Family Member

11.4 Describe any source records that will be used to collect data about subjects (e.g. school records, electronic medical records),.

Response: The identified patients' medical records at Erie County Medical Center (Meditech) will be accessed to confirm antipsychotic medications, antipsychotic medications start date and dose, changes in dose, and other changes in medication. Comorbid medical conditions and medications will also be recorded. The EMR may be accessed throughout the study to confirm any antipsychotic dosing changes and weight at clinic visits (if participant is non-compliant with daily weigh-ins). In addition, HDL, LDL, Triglycerides, Total cholesterol and AC1 information will be gathered from the records throughout the baseline, treatment, and follow-up periods.

11.5 Indicate whether or not *individual* subject results, such as results of investigational diagnostic tests, genetic tests, or incidental findings will be shared with subjects or others (e.g., the subject's primary care physician) and if so, describe how these will be shared.

Response: The participants will be aware of their test results because they will be weighing themselves daily.

11.6 Indicate whether or not study results will be shared with subjects or others, and if so, describe how these will be shared.

Response: Study results will be shared with the patients and their parents at the end of the follow-up. These will be shared with a letter and an invitation to contact one of the study team members ([name] or [name]) for any questions. The aggregate data will be presented at conferences and in publications and other presentations.

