17.0 Data Management and Analysis*

17.1 Describe the data analysis plan, including any statistical procedures. This section applies to both quantitative and qualitative analysis.

Response: The project is a multiple baseline single case experimental design, with a 2 month baseline data collection. Families will then be randomized to staggered initiation of treatment in blocks of 4 families. We anticipate having 8 participating families at the

beginning of the project and would randomly assign them to start the baseline assessment between 1 and 9 weeks into the project, with the treatment then beginning between weeks 9 and 17. Treatment completion for this initial cohort would be between weeks 21 and 29, and the final follow-up would occur between weeks 29 and 37. Families entering NAVIGATE after the recruitment of the first cohort will be randomly assigned to start the baseline from 1 to 9 weeks after entry. This will provide a significant baseline (2 months) for all participants with different initial points for the study.

Analysis of the daily weights will involve discontinuous growth curve analysis using multi-level modeling (Singer and Willet, 2003). Separate models are developed for each participant which include the daily weights from the baseline (60 days), treatment (90 days) and follow-up (60 days) phases. Given the nature of the data, we would hypothesize significantly different slopes for the baseline vs treatment phases. We would also expect no significant differences between the slopes for the treatment phase and the follow-up phase. The primary analysis involves modeling each individual as a level one variable.

17.2 *If applicable, provide a power analysis.*

NOTE: This may not apply to certain types of studies, including chart/records reviews, survey studies, or observational studies. This question is asked to elicit whether the investigator has an adequate sample size to achieve the study objectives and justify a conclusion.

Response: NA

17.3 *Describe any procedures that will be used for quality control of collected data.*

Response: Data will be reviewed by trained and IRB approved study personnel.

18.0 **Confidentiality***

A. Confidentiality of Study Data

Describe the local procedures for maintenance of confidentiality of study data and any records that will be reviewed for data collection.

A

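### The per-patient slope test in 17.1 does not use the antipsychotic changes recorded under 11.4, so a drug stop between about mid-baseline and mid-treatment can pass for a program effect in a patient still gaining weight

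*Combined protocol and SAP*

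**What the plan says.** Section 17.1 describes the analysis of the primary endpoint, weight: "Separate models are developed for each participant which include the daily weights from the baseline (60 days), treatment (90 days"; the sentence goes on to the 60 follow-up days. The hypothesis is that "we would hypothesize significantly different slopes for the baseline vs treatment phases", and "The primary analysis involves modeling each individual as a level one variable". The section names no medication covariate, sensitivity analysis or plot.

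Under section 11.4 the chart will be used to "confirm antipsychotic medications, antipsychotic medications start date and dose, changes in dose, and other changes in medication". It adds: "The EMR may be accessed throughout the study to confirm any antipsychotic dosing changes and weight at clinic visits". No section says how these data enter the analysis. Section 6.2 says "the medication that patients are taking will be managed by their physician and only be a screening criteria", but that answers a question about drug handling.

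Section 22.1 gives the reason to care: "Patients who are prescribed antipsychotics often gain significant weight and commonly stop the medication as a result. This can precipitate further psychotic episodes". Section 4.1 says weight on antipsychotics keeps rising over the first year and then stabilises. Section 20.1 does not withdraw a patient for stopping the drug, so such a patient stays in the analysis.

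The design has one protection, in section 17.1: "Families will then be randomized to staggered initiation of treatment in blocks of 4 families". Every patient nevertheless has the same two-month baseline before treatment.

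**The concern.** The protocol names a common event, stopping the drug because of weight gain, that can itself change the primary endpoint. It plans to record at least the stops the clinic knows of, and then leaves them out of the comparison. The test contrasts two slopes within one person. If the drug was driving the baseline slope and is stopped near the switch to treatment, the slope falls whether or not the program works. What is at stake is the reading of individual results, which are the unit of the primary analysis.

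**Working it through.** The plan states no effect size, power or alpha (17.2 is marked not applicable), so there is no figure to reproduce. The check asks how large a false slope change a drug stop can produce.

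**Inputs from the protocol**
- Gain on olanzapine in first-episode adults (4.1): 10.34 lb in 12 weeks, so g = 10.34/12 = 0.862 lb/week.
- Benefit in the cited randomised first-episode trial (4.1): (15.2 - 9.0)/13 weeks = 6.2/13 = 0.477 lb/week.
- Phases (17.1): days 0-59 baseline, 60-149 treatment, 150-209 follow-up.
- Patients (1.0): 12.

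**Assumptions:** steady gain g until a lasting stop on day d, flat weight afterwards, no program effect.

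**Two readings of the model**, since 17.1 does not fix the form: (a) a separate line in each phase; (b) joined lines, y = b0 + b1·t + b2·max(t-60, 0) + b3·max(t-150, 0). The contrast is treatment slope minus baseline slope, which is b2 in (b).

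**Hand check for (a).** If weight rises for a share f of a phase and is then flat, the fitted slope is about g·f²(3-2f).
- Day 30: baseline f = 1/2, slope 0.862 × 0.25 × 2 = 0.43; treatment slope 0; contrast -0.43 (exact daily fit -0.44).
- Day 60: baseline 0.86, treatment 0; contrast -0.86.
- Day 90: treatment f = 1/3, slope 0.862 × 0.111 × 2.333 = 0.22; contrast 0.22 - 0.86 = -0.64 (exact -0.63).

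**Exact fits, lb/week**

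| Stop day | (a) separate | (b) joined |
|---|---|---|
| 15 | -0.14 | -0.12 |
| 30 | -0.44 | -0.37 |
| 60 | -0.86 | -0.86 |
| 90 | -0.63 | -0.80 |
| 120 | -0.22 | -0.38 |
| 150 | 0 | 0 |

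The error reaches 0.477 for stops on days 32-101 (a) or 36-113 (b). It can do so only if g is at least 0.477 (a) or 0.453 (b), that is 55% or 53% of the olanzapine rate.

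**If weight falls after the stop** (assumed: half of g for 8 weeks, then flat; the documents give no post-stop course), (a)/(b):
- day 5: +0.40/+0.41
- day 15: +0.20/+0.28
- day 30: -0.32/-0.14
- day 60: -1.16/-1.07

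So the size and even the sign depend on the stop day and on the course afterwards. A stop at day 15 with a restart at day 75 gives +0.65/+0.79 (flat while off the drug).

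**Would it be declared significant?** This depends on day-to-day noise, which the documents do not give. In simulations of the 60 baseline and 90 treatment days with a stop at day 60, a slope fall was flagged (z below -1.96) in 85-90% of runs with SD 2 lb and lag-1 correlation 0.7. With SD 3 lb and correlation 0.9 the figure was 20-21%. At a plateau it was 1-4%, no real excess over the nominal 2.5%.

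**Group mean of 12.** One stop at day 60 moves it by 0.862/12 = 0.07, or 1.16/12 = 0.10 if weight falls. Three move it by 3 × 0.862/12 = 0.22. Reaching 0.477 takes 0.477 × 12/0.862 = 6.6, so seven patients (flat case).

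**What adjustment can do.** A slope change at the true date returns the program effect to zero, but only because the fitted model is then the generating one. At day 60 exactly the model cannot be fitted. Elsewhere the standard error of the program term grows as follows (ranges over (a), (b) and assumed AR(1) correlation 0 to 0.8):
- one change 14 days from treatment start: 3.3-5.3 times
- one change 30 days away: 1.7-2.1 times
- changes at days 30 and 75: 4.3-4.7 times
- changes at days 45 and 75: 6.1-7.1 times

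If weight responds 14 days late, adjusting at the recorded date leaves -0.48/-0.37 for a stop at day 30 and +0.23/+0.22 for one at day 90.

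**The case against.** This is a 12-patient pilot with no power claim. Staggered random starts and replication across families are the standard defence of a multiple-baseline design, and one stopper barely moves the group mean. Many of the 40-45 patients already in the program may have passed the first year and plateaued. Psychiatric visits continue (19.1), and the program director is a co-investigator, so stops known to the clinic should reach the chart. All of this stands, and it confines the point to individual results in patients still gaining. It does not remove the point: 17.1 models each person, staggering guards against shared calendar events rather than a personal drug stop, and even charted stops are not used.

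A reader might infer more than the documents support:
- *Every lasting stop flatters the program.* This holds only if weight stays flat afterwards; an early-baseline stop can do the opposite.
- *The group conclusion is unsafe.* No stop rate is given, and in the flat illustration seven of 12 patients would have to stop at treatment start for the mean to shift by the cited benefit.
- *Stops are hidden from the clinic.* The procedures in 11.1-11.3 list no question on drug-taking, but 22.1 does not say that stops are concealed.
- *Medication changes may go uncollected.* 11.4 already says the chart will be accessed for them. Only the timing across phases is loosely worded.

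**Conclusion.** The point holds, limited to individual results. Followed as written, 17.1 can attribute to the program a slope change caused by a lasting drug stop between about mid-baseline and mid-treatment. With the olanzapine rate, flat weight after the stop and no program effect, the false change is about 0.4 to 0.9 lb/week for stops from day 30 to day 90, comparable with or above the 0.48 lb/week of the cited trial. These figures illustrate and do not bound: the day-60 error is larger if weight falls after the stop, smaller at lower rates of gain, and zero if weight has plateaued and stays flat. How many patients are affected is unknown. The plan should be changed, but this does not invalidate the design.

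**What to change.** 1. **Section 17.1, display.** Mark all recorded antipsychotic starts, stops, switches and dose changes on each patient's weight plot.
2. **Section 17.1, sensitivity analysis.** Add a descriptive analysis that puts a slope change in that patient's model at starts, stops and major switches, keeping all days. Run it at the recorded date and again two weeks later, because weight may respond late. Do not add a term for every dose change; the extra terms cost too much precision.
3. **Section 17.1, reporting rule.** Report a patient's result as not separable from the medication change when a change falls within about two weeks of treatment start, or when the added terms greatly inflate the standard error of the program term (for example, more than threefold).
4. **Section 11.4.** State that medication-change dates are abstracted for every patient across baseline, treatment and follow-up, as is already stated for the laboratory values.

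These steps use data already planned and cost a few sentences. The limit is that the analysis stays descriptive and sees only charted changes. A short question on drug-taking at planned contacts is optional. It could reach stops unknown to the clinic, but recall is imperfect, a patient may conceal a stop, and asking weekly during treatment may itself alter drug-taking.

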23.0 Compensation for Research-Related Injury

N/A: The research procedures for this study do not present risk of research related injury (e.g. survey studies, records review studies). This section does not apply.

23.1 If the research procedures carry a risk of research related injury, describe the available compensation to subjects in the event that such injury should occur.

Response:

23.2 Provide a copy of contract language, if any, relevant to compensation for research related injury.

*NOTE: If the contract is not yet approved at the time of this submission, submit the current version here. If the contract is later approved with **different language regarding research related injury**, you must modify your response here and submit an amendment to the IRB for review and approval.*

Response:

24.0 Economic Burden to Subjects

24.1 *Describe any costs that subjects may be responsible for because of participation in the research.*

NOTE: Some examples include transportation or parking.

Response: Participants will have travel and parking costs. Payments received for participation in research are considered taxable income.

N/A: This study is not enrolling subjects, or is limited to records review procedures only. This section does not apply.

25.0 Compensation for Participation

27.1 *Describe the amount and timing of any compensation to subjects, including monetary, course credit, or gift card compensation.*

Response: Patients and parents will receive one dollar for each day that they submit a weight measurement during the study, for a maximum of \$210 each. They will also receive \$25 each for each of the 3 assessments.

N/A: This study is not enrolling subjects, or is limited to records review procedures only. This section does not apply.

N/A: There is no compensation for participation. This section does not apply.

26.0 Consent Process

26.1 *Indicate whether you will be obtaining consent.*

NOTE: This does not refer to consent documentation, but rather whether you will be obtaining permission from subjects to participate in a research study. Consent documentation is addressed in Section 29.0.

Yes *(If yes, Provide responses to each question in this Section)*

No *(If no, Skip to Section 29.0)*

26.2 *Describe where the consent process will take place. Include steps to maximize subjects' privacy.*

Response: The participant and the family member will be consented separately in a private office in the clinic. The patient will be consented first, and if the patient agrees, the family member will then be consented.

26.3 *Describe how you will ensure that subjects are provided with a sufficient period of time to consider taking part in the research study.*

NOTE: It is always a requirement that a prospective subject is given sufficient time to have their questions answered and consider their participation. See “SOP: Informed Consent Process for Research (HRP-090)” Sections 5.5 and 5.6.

Response: Potential subjects will be offered the opportunity to participate in the trial. If interested, research staff will review the consent form with potential subjects at their convenience. Potential subjects are encouraged to review the consent form and are permitted to take a copy home/keep a copy for review prior to signing. Potential subjects are also encouraged to discuss participation with their primary care doctor or treating psychiatrist.

26.4 Describe any process to ensure ongoing consent, defined as a subject’s willingness to continue participation for the duration of the research study.

Response: Ongoing consent will be assessed at the weekly sessions.

26.5 Indicate whether you will be following “SOP: Informed Consent Process for Research (HRP-090).” Pay particular attention to Sections 5.4-5.9. If not, or if there are any exceptions or additional details to what is covered in the SOP, describe:

- *The role of the individuals listed in the application who are involved in the consent process*
- *The time that will be devoted to the consent discussion*
- *Steps that will be taken to minimize the possibility of coercion or undue influence*
- *Steps that will be taken to ensure the subjects’ understanding*

Response:

We have reviewed and will be following “SOP: Informed Consent Process for Research (HRP-090).”

Non-English Speaking Subjects

N/A: This study will not enroll Non-English speaking subjects.
(*Skip to Section 28.8*)

26.6 Indicate which language(s) other than English are likely to be spoken/understood by your prospective study population or their legally authorized representatives.

NOTE: The response to this Section should correspond with your response to Section 8.4 of this protocol.

Response:

26.7 *If subjects who do not speak English will be enrolled, describe the process to ensure that the oral and written information provided to those subjects will be in that language, how you will ensure that subjects are provided with a sufficient period of time to consider taking part in the research study, and any process to ensure ongoing consent. Indicate the language that will be used by those obtaining consent.*

NOTE: Guidance is provided on “SOP: Informed Consent Process for Research (HRP-090).”

Response:

Cognitively Impaired Adults

N/A: This study will not enroll cognitively impaired adults.
(Skip to Section 28.9)

26.8 *Describe the process to determine whether an individual is capable of consent.*

Response:

Adults Unable to Consent

N/A: This study will not enroll adults unable to consent.
(Skip to Section 28.13)

*When a person is not capable of consent due to cognitive impairment, a legally authorized representative should be used to provide consent (Sections 28.9 and 28.10) **and, where possible, assent of the individual should also be solicited** (Sections 28.11 and 28.12).*

26.9 *Describe how you will identify a Legally Authorized Representative (LAR). Indicate that you have reviewed the “SOP: Legally Authorized Representatives, Children, and Guardians (HRP-013)” for research in New York State.*

NOTE: Examples of acceptable response includes: verifying the electronic medical record to determine if an LAR is recorded.

Response:

We have reviewed and will be following “SOP: Legally Authorized Representatives, Children, and Guardians (HRP-013).”

26.10 For research conducted outside of New York State, provide information that describes which individuals are authorized under applicable law to consent on behalf of a prospective subject to their participation in the research. One method of obtaining this information is to have a legal counsel or authority review your protocol along with the definition of “legally authorized representative” in “SOP: Legally Authorized Representatives, Children, and Guardians (HRP-013).”

Response:

26.11 Describe the process for assent of the adults:

- *Indicate whether assent will be obtained from all, some, or none of the subjects. If some, indicate which adults will be required to assent and which will not.*

Response:

- *If assent will not be obtained from some or all subjects, provide an explanation of why not.*

Response:

26.12 Describe whether assent of the adult subjects will be documented and the process to document assent.

NOTE: The IRB allows the person obtaining assent to document assent on the consent document using the “Template Consent Document (HRP-502)” Signature Block for Assent of Adults who are Legally Unable to Consent.

Response:

Subjects who are not yet Adults (Infants, Children, and Teenagers)

N/A: This study will not enroll subjects who are not yet adults.
(Skip to Section 29.0)

26.13 Describe the criteria that will be used to determine whether a prospective subject has not attained the legal age for consent to treatments or procedures involved in the research under the applicable law of the jurisdiction in which the research will be conducted (e.g., individuals under the age of 18 years). For research conducted in NYS, review “SOP: Legally Authorized Representatives, Children, and Guardians (HRP-013)” to be aware of which individuals in the state meet the definition of “children.”

NOTE: Examples of acceptable responses include: verification via electronic medical record, driver's license or state-issued ID, screening questionnaire.

Response: Patient's age is noted in the clinical record. [name] will inform research staff if a patient is under the age of 18.

26.14 *For research conducted outside of New York State, provide information that describes which persons have not attained the legal age for consent to treatments or procedures involved the research, under the applicable law of the jurisdiction in which research will be conducted. One method of obtaining this information is to have a legal counsel or authority review your protocol along the definition of "children" in "SOP: Legally Authorized Representatives, Children, and Guardians (HRP-013)."*

Response:

26.15 *Describe whether parental permission will be obtained from:*

Response:

- One parent even if the other parent is alive, known, competent, reasonably available, and shares legal responsibility for the care and custody of the child.
- Both parents unless one parent is deceased, unknown, incompetent, or not reasonably available, or when only one parent has legal responsibility for the care and custody of the child.
- Parent permission will not be obtained. A waiver of parent permission is being requested.

NOTE: The requirement for parent permission is a protocol-specific determination made by the IRB based on the risk level of the research. For guidance, review the "CHECKLIST: Children (HRP-416)."

26.16 *Describe whether permission will be obtained from individuals **other than parents**, and if so, who will be allowed to provide permission. Describe your procedure for determining an individual's authority to consent to the child's general medical care.*

Response: Permission will be sought from parents or legal guardians. As the patient's clinical provider, [name] will have information as to who has the authority to consent to the adolescent's health care. This information will be provided to the research staff at the time of referral.

26.17 *Indicate whether assent will be obtained from all, some, or none of the children. If assent will be obtained from some children, indicate which children will be required to assent.*

Response: Assent will be obtained from any children participating in the study.

26.18 When assent of children is obtained, describe how it will be documented.

Response: At the time of the consent procedure, patients and parents will be separated. The patient will be asked to sign the assent or consent form, and provided the patient signs, the parent will then be asked to sign the consent form.

